Our central hypothesis is that the attending nurse will enhance critical patient-centered elements of care that will in turn improve patient education and shared decision-making, medication adherence, stroke-related health literacy, and reduce early readmissions to ultimately yield improved patient quality of life. Our primary objective is to determine whether the attending nurse model of care improves stroke patients' health at 7 days, 30 days, and 90 days after hospital discharge as assessed through questionnaires.

**Number of
Patients**

372 patients

Main Inclusion and Exclusion Criteria	
We will include all adult patients admitted to the Vascular Neurology Service with a clinical diagnosis of stroke, brain hemorrhage, or transient ischemic attack.
 
We will exclude patients whose level of care is limited to comfort care or hospice, those with severe dementia prior to admission, and those who are both non-communicative and have no family or other social support.

Investigational Product	
None
 
This is a comparative effectiveness study comparing two models of nursing care delivery to stroke patients (attending nurse model vs. conventional inpatient nursing care)

Duration of administration (if applicable)	
The duration of the intervention phase will depend on the duration of a patient's hospital admission.

Reference therapy	
The reference therapy is standard inpatient nursing care.

Statistical Methodology	
Our primary outcome will be scores on scales of medication adherence and stroke education retention. The scores on these tests will be compared between patients who were assigned to the attending nurse model of care versus standard nursing care.
 
Secondary outcomes will include comparisons between groups of the thirty day readmission rate, scores on a patient-centered stroke impact scale, 2 modified quality of life scales, results of a newly designed series of 13 Likert style questions, and a global statistic that includes the results of all scales.

Safety Evaluations	
All enrolled patients will be evaluated via telephone interview at 7, 30, and 90 days following hospital discharge and screened for major cardiovascular and cerebrovascular events. While in the hospital, subject safety will be assured via already existent quality assurance mechanisms.

Data and Safety Monitoring Plan	
The PIs will be responsible for monitoring the data quality and the ongoing safety of patients.

1 BACKGROUND AND STUDY RATIONALE

This document is a clinical research protocol and the described study will be conducted in compliance with the protocol, Good Clinical Practice standards, associated federal regulations, and all applicable University of Pennsylvania Research Policies and Procedures and all applicable Federal and state laws and regulations.

Introduction

Stroke is a leading cause of morbidity and mortality in the United States. Hospital units dedicated to stroke care have been shown to improve patient outcomes compared to other units,¹ but the optimal models of care delivery within stroke units have not been well studied, particularly in a patient-centered context. We propose to study the role of an attending nurse in the inpatient stroke unit compared to standard nursing care. The attending nurse will serve as a continuous source of support for stroke patients and families, communicate the plan of care, and provide education.

1.1 Background and Relevant Literature

Every year, approximately 610,000 people experience a first stroke and another 185,000 have a recurrent stroke in the United States.² Further, among 307,887 ischemic stroke patients in a Medicare database, 14% were readmitted to hospitals within 30 days of discharge.³ Stroke patients are thus a high risk population worthy of increased treatment interventions to prevent early complications. Patients with recurrent stroke have poorer outcomes and higher healthcare costs than those with first stroke.⁴ Despite the substantial burden of recurrent stroke, many patients with prior strokes are ill informed about stroke risk factors and have suboptimal personal health behaviors.^{5,6} Existing care delivery models thus may not optimally aligned with stroke patients' needs and goals.

Poor adherence to prescribed medications following hospital discharge likely plays an important role in stroke recurrence, disability, other complications, and death.⁷ In the largest observational study of medication compliance following stroke, the Adherence eValuation After Ischemic stroke–Longitudinal (AVAIL) registry, independent predictors of 1-year medication persistence included fewer medications prescribed at discharge, having an adequate income, having an appointment with a provider, and a greater understanding of why medications were prescribed and possible side effects.⁸ Earlier studies have also noted that inadequate care transitions and poor patient–provider communications contribute to medication non-adherence.⁹ Unfortunately, no educational or organizational interventions have clearly been shown to effectively improve adherence to secondary stroke prevention strategies.¹⁰

Attending Nurse

The attending nurse model of in-hospital care delivery may work to improve patient understanding, shared decision-making, medication adherence, and reduce early readmissions after discharge to ultimately yield improved patient quality of life. The care delivered and directed by the attending nurse will be guided by the principles of relationship based nursing developed by Koloroutis in which commitment to care and service to patients hinges upon a therapeutic relationship.¹¹ On the inpatient stroke unit, the attending nurse will take ownership of essential aspects of an individual stroke patient's care, education, and transition out of the hospital. By serving as the patient care coordinator, advocate, and educator, the attending nurse will be able to create a deep and meaningful therapeutic relationship with patients. To further contribute to the patient's plan of care, the attending nurse will be present on daily teaching rounds.

Allowing nurses to function as attending nurses is in keeping with the dictates of the Institute of Medicine recommendation to have nurses practice to the full extent of their education and training as well as treating nurses as full partners in redesigning health care.¹² Though an attending nurse has been studied in outpatient settings,¹² this model of care has not been used extensively for inpatient care.¹³ Quantitative data for the effect of an attending nurse on inpatient care are lacking, but qualitative data suggest that

attending nurses ameliorated shared decision making with patients, resulting in a more proactive, confident and informed relationship between patients and providers.^{13,14} Feedback from nursing staff and administrators after an attending nurse model was launched at other institutions revealed no negative consequences.^{13,14} To our knowledge, the attending nurse model has not been studied in any disease-specific inpatient population. Stroke is potentially an ideal disorder for this model of care because of its medical complexity, individual patient burden, and high early risk of recurrence, yet is amenable to aggressive preventative and rehabilitative measures.

1.2 Name and Description of the Investigational Product

There is no investigational product. We are investigating which model of nursing care is most effective: the attending nurse model, as detailed above, or the standard care model. The tasks performed by the attending nurse for each patient will be documented during the patients' hospitalization to assure individual patient goals are being met. Patients who receive care from the attending nurse will be compared to those who are cared for by staff nurses alone.

1.2.1 Clinical Data to Date:

For 3-4 months, the attending nurse model has been in use on the vascular Neurology inpatient service for some patients. No patient has ever refused care from the attending nurse and we have noticed no in-house complications from attending nurse care as evaluated by standard quality metrics. Additionally, we have piloted our survey instruments. The instruments take a median of 15 minutes to administer.

Stroke readmissions at our institution over the past 2 years were estimated from the GWTG registry at our center. Our readmission rates (~10%) are lower than the national average (~15%) for stroke patients.

2 Study Objectives

2.1 Primary Objective

- To determine whether patients report better understanding of stroke facts and medication adherence when cared for by an attending nurse compared to routine nursing care.

2.2 Secondary Objectives (if applicable)

- To determine whether a nurse attending model of care improves overall outcome following stroke or TIA
- To determine whether newly devised questions focused on the inpatient experience as well as patient satisfaction can detect valid differences between treatment groups.
- To assess whether an attending nurse improves patient perception of deficits and quality of life compared to routine nursing care.
- To assess whether an attending nurse reduces patient readmission rates compared to standard nursing care.

3 Investigational Plan

3.1 General Design

We propose a phase III comparative effectiveness study to evaluate the added value of an attending nurse to the inpatient care of stroke patients compared to routine care. Both types of care are currently available on the inpatient Vascular Neurology service at the Hospital of the University of Pennsylvania as well as at other institutions. Currently, the nurse attending works randomly with patient she selects based on her availability.

In the standard model of inpatient nursing care, stroke education is provided largely in the form of pamphlets distributed to patients and their families. Patients are cared for by a team of physicians and staff nurses with access to social workers and case managers, however, staff nurses do not routinely round on their patients with other members of the care team.

Screening of patients for this trial will occur once the clinical decision to admit a patient to the Vascular Neurology service has been made. All patients who meet inclusion criteria will be assigned to a study arm, addition of an attending nurse versus routine nursing care, according to the day of the week they are admitted to the hospital. Patients who are admitted on even numbered week days will have their care supplemented by the attending nurse. This is effectively a stratified random assignment, as there are no clinical or systematic features that otherwise are associated with odd or even numbered days. The duration of the intervention will depend on the duration of a patient's hospital admission.

To compare the two models of nursing care, we will survey all patients directly about the care they receive in the hospital once they are discharged. Surveys tools designed to ascertain medication adherence, disease specific knowledge, as well as satisfaction with care and hospital readmissions will be assessed at 7, 30, and 90 days via follow-up structured telephone interviews. We will consider the 7 day follow-up phone call the baseline assessment. The Morisky scale (MMAS-4),¹⁵ a well validated tool that has been studied in stroke victims,¹⁶ will be used to determine medication adherence. The Stroke Patient Education Retention (SPER)¹⁷ tool will be used to assess patient knowledge. The Stroke Impact Scale (SIS)¹⁸ will be used to evaluate self-perception of stroke deficits by patients. Thirteen other survey questions designed specifically for this study will also be posed to patients at 7, 30 and 90 days from follow up along with two overall quality of life questions at 7 and 90 days. As a secondary outcome, we will calculate and then use a global statistic as a general marker for success to compare the effectiveness of each nursing care model in improving patients' overall outcomes.¹⁹ All interviews will be performed by a trained research assistant who will not be involved in the inpatient care of patients and will be blinded to study allocation. Subject participation will conclude after 90 days.

We will request a waiver of consent for initial enrollment in this study. Follow-up calls to patients will explicitly state according to an IRB-approved script that the questions are part of a research study. Patients will also be asked if they consent to collection of data from their medical record as part of the study. Patients will have the option to participate or decline. If they choose to participate in the interview survey and allow collection of data from their recent hospitalization, then the study will proceed with their verbal consent.

If they decline to participate in the interview survey, then no further study specific tools will be used, but they will be asked if they consent to chart abstraction. However, patients cannot participate in interviews without agreeing to data collection. Patients can decline to participate in both the interviews and allow for data collection. If they fully decline to participate in the study, their data will be expunged and no further data collected.

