3.1.3 Allocation to Interventional Group

Stroke patients who are admitted on even-numbered weekdays and enrolled in this trial will be assigned to care with an attending nurse; patients admitted on odd-numbered weekdays will get usual routine care. The attending nurse will query the electronic medical record as well as communicate with the physician team so that all incoming admissions on even-numbered days to the Vascular Neurology service are known to the attending nurse.

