6.2 Study Intervention Phase

If patients satisfy inclusion criteria and lack exclusion criteria they will be assigned to the intervention arm or the control arm depending on their admission date. The intervention phase will be the duration of the patient's hospital stay.

No research related procedures that differ from standard of care will be conducted as this is a comparative effectiveness trial.

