7.3 Sample Size and Power Determination

For this pilot project, we anticipate that 65% of patients in the control arm will be adherent to medications (MMAS-4 < 2) based on literature reporting 60%¹⁶ adherence as evaluated using these scales in stroke patients and 70%²¹ adherence in patients with hypertension. To achieve success on the primary endpoint, we estimate that patients must improve to by 15% in order to make this intervention worthy of future investigation in a larger study. Assuming an alpha of 0.05 and a power of 80%, with a 1:1 assignment to each arm, we will require 186 patients in each arm for a total of 372 patients. With that number of patients

we will be able to powered to detect a very small difference of 0.3 (delta = .15 (SD=2)) in the mean scores of the SPER based on the published data.¹⁷ Each outcome will be evaluated independently so that we will not need to make any power readjustments. Readmission rates at 30 days are typically low⁴ and likely lower at our institution based on prior data so we will be underpowered for this outcome. Clinically differences on the SIS will depend on the initial stroke severity of patients within each group and therefore the study cannot be powered for this secondary endpoint.

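### No allocation rule covers weekend admissions; if week days means Monday to Friday, section 3.1 sends every weekend patient to the control arm by implication

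*Combined protocol and SAP*

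**What the plan says.** Four places in the protocol bear on allocation.

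- Section 3.1 covers everyone: "All patients who meet inclusion criteria will be assigned to a study arm", and it does so "according to the day of the week they are admitted to the hospital". The route to the intervention is: "Patients who are admitted on even numbered week days will have their care supplemented by the attending nurse". No rule for the control arm is written there. The method is defended as effectively random because "there are no clinical or systematic features that otherwise are associated with odd or even numbered days".
- Section 3.1.3 names both arms. For the intervention: "Stroke patients who are admitted on even-numbered weekdays and enrolled in this trial will be assigned to care with an attending nurse". For control: "patients admitted on odd-numbered weekdays will get usual routine care". The next sentence has the nurse informed of admissions on even-numbered days, with no limit to weekdays.
- Section 6.2 says of eligible patients that "they will be assigned to the intervention arm or the control arm depending on their admission date". It gives no odd/even rule and no weekday limit.
- Sections 4.1 and 4.2 contain no criterion on day of admission.

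Three further sections matter. Section 5.1 has the nurse meet patients within 24 hours of admission. Section 5.2 has her see them on weekdays, and sends even-weekday patients to routine care once she has 8 patients. Section 7.3 sizes the trial "with a 1:1 assignment to each arm".

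**The concern.** Section 3.1 has two arms, assigns everyone, and opens one route to the nurse. If week days means Monday to Friday, a weekend patient can only land in routine care. The control arm would then be odd-weekday patients plus all weekend patients, against a nurse arm drawn from weekdays alone.

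The argument in section 3.1 that allocation is as good as random concerns odd against even days. It says nothing about weekend against weekday. Section 7.4 plans unadjusted t-tests and a chi-square test on all patients, so any difference between weekend and weekday patients that has nothing to do with the nurse would be read as part of the nursing effect. Section 7.5 defines the intention-to-treat population as everyone who undergoes assignment, so the same unwritten rule also decides who is analysed.

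**Working it through.** **The plan's own figure.** Section 7.3 gives 186 per arm for 65% versus 80% adherence, alpha 0.05, power 80%, 1:1. The usual two-sided formula gives

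n = [1.96·√(2 × 0.725 × 0.275) + 0.842·√(0.65 × 0.35 + 0.80 × 0.20)]² / 0.15² = 138 per arm, or 151 with continuity correction.

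So 186 does not reproduce. That is a separate matter; the total of 372 is taken as given below.

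**Inputs.** Total 372, and 65% versus 80% (reading the 15% improvement as percentage points), from section 7.3; 700 to 800 admissions a year and 7 months, from section 4.5. Three assumptions are not in the documents: a weekend share w of 15% up to 2/7 = 28.6% (uniform admissions); half of weekday dates even; and no use of the overflow rule in section 5.2.

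**Split if weekend patients go to routine care.**

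- Nurse arm = 372 × (1 − w)/2; control arm = 372 − nurse arm.
- Weekend share of controls = w / [w + (1 − w)/2].
- Power = Φ{[0.15 − 1.96·√(p̄q̄(1/n₀ + 1/n₁))] / √(0.65 × 0.35/n₀ + 0.80 × 0.20/n₁)}, where n₀ is control, n₁ is nurse, p̄ is the pooled proportion and q̄ = 1 − p̄.

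| Weekend share | Nurse | Control | Weekend share of controls | Power |
|---|---|---|---|---|
| 1:1 as planned | 186 | 186 | – | 90.3% |
| 15% | 158 | 214 | 26% | 89.5% |
| 20% | 149 | 223 | 33% | 88.9% |
| 25% | 140 | 232 | 40% | 88.1% |
| 28.6% | 133 | 239 | 44% | 87.4% |

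Weekend patients are 0% of the nurse arm in each of the last four rows.

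**Bias.** If weekend and weekday patients differ in adherence by d points for reasons unrelated to the nurse, the control rate shifts by d times the weekend share of controls. Under uniform admissions, 0.444 × 5 = 2.2 points and 0.444 × 10 = 4.4 points. At a 15% weekend share, 0.261 × 5 = 1.3 and 0.261 × 10 = 2.6. The values of d are illustrative. At the top, 4.4 points is 4.4/15 = 30% of the 15-point target.

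**Another meaning of even.** Section 3.1 allocates by day of the week and section 6.2 by admission date. If days of the week are numbered from Monday = 1 and only Monday to Friday counts, the nurse gets Tuesday and Thursday. Under uniform admissions her share is 2/7, the split is about 106:266 and power is 82.9%.

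**Recruitment if only weekday admissions count.** Under uniform admissions, 7 months yields 700 × 7/12 × 5/7 = 292 to 800 × 7/12 × 5/7 = 333 patients. Reaching 372 takes 372/(800/12 × 5/7) = 7.8 to 372/(700/12 × 5/7) = 8.9 months. At a 15% weekend share it takes 372/(800/12 × 0.85) = 6.6 to 372/(700/12 × 0.85) = 7.5 months. All of these treat every admission as eligible and consenting.

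**The case against.** A reader might infer that the protocol gives weekend patients three conflicting allocations (routine care in 3.1, no arm in 3.1.3, either arm in 6.2) that cannot all be followed. The documents do not support that. No section names weekends. Section 3.1 states no default to routine care; it follows only by implication. Section 6.2 is a one-line summary that does not say weekend patients may enter either arm. A rule of even weekdays to the nurse and everyone else to routine care satisfies 3.1 and 6.2 and contradicts nothing in 3.1.3. The case is unspecified rather than contradictory. That consistent rule is, however, the one that produces the confounding.

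The Monday-to-Friday reading is also not the only one. The justification in 3.1 and the notification sentence in 3.1.3 speak of odd or even days without a weekday limit, and 7.3 assumes 1:1; both would fit parity on any day. This stands, and it is why the figures above are conditional. Against it, the nurse's weekday visits and 24-hour first contact in 5.1 and 5.2 fit poorly with weekend patients entering her arm.

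The caseload cap in 5.2 means that 1:1 is not assured on any reading, so weekends are not the only threat to the ratio. Finally, the documents give no evidence that weekend patients differ in adherence or stroke knowledge. The bias is potential, and its size is an assumption.

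**Conclusion.** The point holds as a missing rule with a harmful natural reading. The allocation of weekend admissions is undefined, sections 3.1, 3.1.3 and 6.2 support different readings, and the Monday-to-Friday reading of 3.1 yields a structurally unbalanced comparison. With a weekend share of 15% to 28.6% and half of weekday dates even, the split is about 158:214 to 133:239, and weekend patients are about 26% to 44% of controls and none of the nurse arm.

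A reader might take this as a power problem. It is not: power for 65% versus 80% at 372 patients stays between 87.4% and 89.5% over that range, against 90.3% at 1:1. The harm is possible bias, about 2.2 to 4.4 points in the control adherence rate under uniform admissions if weekend patients differ by 5 to 10 points. It should be corrected before enrolment, because once patients have been allocated this way the nurse arm holds no weekend patients to compare with.

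**What to change.** Reconcile sections 3.1, 3.1.3, 4.1/4.2, 5.1, 5.2 and 6.2 into one allocation rule that treats weekend admissions the same way in both arms: no weekend patient is counted as a control unless weekend patients can equally enter the nurse arm. State whether odd and even refer to the calendar date or to a numbered day of the week. Then restate the expected allocation ratio in 7.3 and the recruitment time in 4.5. The choice of rule is the sponsor's.

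The change is mainly wording, but each option has a cost. If only weekday admissions are counted, weekend patients no longer contribute: 372 patients would take about 7.8 to 8.9 months under uniform admissions, against the planned 7 (about 6.6 to 7.5 if the weekend share is 15%). If weekend patients are assigned by date to both arms, the rule must be reconciled with the 24-hour first contact in 5.1 and the weekday visits in 5.2.

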3.1.1 Screening Phase

Patients will be screened upon admission to the Vascular Neurology non-intensive care unit service. As part of standard intake procedures, a physician on the admitting team will determine patient study eligibility. There will be no extra evaluations or laboratory tests needed at the screening visit.

As this is a comparison of two effective nursing models, both of which are available and employed in clinical practice, the study is of minimal risk to patients. All patients will receive a standard treatment currently in use at our facility. Patients may be unaware of our ongoing comparative effectiveness trial while they are hospitalized. However, informed consent will be obtained at the time of follow up phone calls.

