4.2 Exclusion Criteria

- Pregnancy
- Comfort or hospice care
- Severe dementia prior to stroke
- Non-communicative and have no family/social support

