7.4 Statistical Methods

In our primary analysis, we will first compare baseline demographics between groups. For our results section, we will compare all patients in the control group to all patients in the intervention arm for outcomes. Mean scores on the SPER will be compared between groups using student t-tests. We will compare proportions of adherent patients on the MMSA-4 between groups using the Pearson chi-square test. Total scores on the SIS, quality of life questions, and the 13 newly devised questions will be compared between groups using t-tests.

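### Odd/even-day allocation is predictable and unconcealed, so it is not a stratified random assignment, and eligibility is judged when the day already points to the arm

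*Combined protocol and SAP*

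**What the plan says.** Section 3.1 (General Design) assigns patients "according to the day of the week they are admitted to the hospital", with even-numbered weekdays receiving the attending nurse. It then defends the rule: "This is effectively a stratified random assignment, as there are no clinical or systematic features that otherwise are associated with" whether the day is odd or even. Section 3.1.3 repeats the weekday form: "Stroke patients who are admitted on even-numbered weekdays and enrolled in this trial will be assigned to care with an attending nurse". Section 6.2 puts it differently: "they will be assigned to the intervention arm or the control arm depending on their admission date". No section gives a rule for weekend admissions.

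On entry to the study, section 3.1.1 says that "a physician on the admitting team will determine patient study eligibility", as part of normal intake. The exclusions in section 4.2 include "Severe dementia prior to stroke" and being non-communicative without family or social support. Neither has an operational threshold. Section 3.1.3 adds that the attending nurse queries the record and speaks with the physicians "so that all incoming admissions on even-numbered days to the Vascular Neurology service are known to the attending nurse".

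Section 5.2 sends an even-day patient to the routine-care arm if the nurse already has 8 patients. Section 5.3 leaves the investigators and staff nurses unblinded, while the telephone interviewer is blinded.

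Section 7.4 specifies unadjusted tests. For education retention, "Mean scores on the SPER will be compared between groups using student t-tests"; for adherence on the MMAS-4, a Pearson chi-square test is used.

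**The concern.** A parity rule is deterministic. Anyone who knows the rule and the date can name the likely arm before the patient is judged eligible. It contains no chance element and no strata, so the label in section 3.1 is wrong on both counts.

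The justification offered is that odd and even days bring in similar patients. That answers only whether the *admitted* patients differ by day. It does not address whether the *enrolled* patients differ, once a clinician who can see the arm decides who counts as too demented or too poorly supported to take part. Those characteristics plausibly bear on both primary endpoints, stroke knowledge and adherence.

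The caseload cap opens a second route. Even-day patients who arrive when the nurse is full join the control arm, so the comparison partly reflects how busy the service was.

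The causal reading of both primary endpoints depends on allocation. Bias at entry does not shrink as the sample grows, the unadjusted tests do nothing to correct it, and the plan describes no log of eligible and excluded patients by day type that would reveal it.

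**Working it through.** **Is the label supported?**

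| Feature needed | What the documents give |
|---|---|
| Random sequence | None; parity of the admission day (3.1, 3.1.3, 6.2) |
| Strata | None named |
| Concealment until eligibility is settled | None; screening follows the decision to admit (3.1), so the day is already known |
| Eligibility free of judgement | Not fully (3.1.1, 4.2) |
| Arm fixed by the allocation rule alone | No; overridden at 8 patients (5.2) |
| Adjustment for imbalance | None (7.4) |

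**How large could the bias be?** The plan gives no figure for this, so what follows is an illustration.

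Inputs from section 7.3: 65% adherence in control, 186 per arm, alpha 0.05 (taken as two-sided, since sidedness is not stated). Section 4.5 gives 180 per arm, which barely changes the results. The 186 does not follow from 65% versus 80% at 80% power: the usual formula gives 138 per arm, or 151 with continuity correction, and 186 gives 90.3% power. That is a separate matter, and 186 is used here only as the planned size.

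Assumptions: no true effect; 20% of eligible patients have 35% adherence; a fraction x of them is screened out on even days only; enrolment still reaches 186 per arm.

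1. Adherence in the other 80%: (0.65 − 0.20 × 0.35) / 0.80 = 0.725.
2. Even-day adherence with x = 0.5: (0.10 × 0.35 + 0.80 × 0.725) / 0.90 = 0.615 / 0.90 = 0.6833.
3. Spurious difference: 0.6833 − 0.65 = 0.0333, or 3.3 points.
4. Pooled proportion 0.6667. Null standard error: √(2 × 0.6667 × 0.3333 / 186) = 0.04888. Standard error under the biased proportions: √((0.65 × 0.35 + 0.6833 × 0.3167) / 186) = 0.04885.
5. Rejection probability: Φ((0.0333 − 1.96 × 0.04888) / 0.04885) + Φ((−0.0333 − 1.96 × 0.04888) / 0.04885) = 0.1005 + 0.0041 = 0.105.

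Range over x:

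| Share of the low-adherence group screened out on even days | Spurious difference | False-positive rate |
|---|---|---|
| 10% | 0.6 points | 5.2% |
| 25% | 1.6 points | 6.2% |
| 50% | 3.3 points | 10.5% |

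With 744 per arm, four times the size, the last row rises to about 28%. More patients make a fixed bias easier to mistake for an effect.

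**What overflow costs if patients are analysed as first allocated.** Take a true effect of 65% to 80% in patients who receive the nurse. With overflow share o, adherence in the allocated arm is 0.80 − 0.15 × o. At 186 per arm, power is 90.3% with no overflow, 82.7% at o = 10%, 72.4% at 20% and 60.1% at 30%. The overflow share is an assumption.

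**The case against.** The best defence is that little room is left for selection. Section 3.1 has every patient who meets the criteria assigned. Section 4.3 says there is no formal recruitment, and consent is waived at admission, so no patient chooses an arm and no recruiter can persuade selectively. The exclusion list is short, and comfort or hospice care is a care status rather than an impression. The interviewer is blinded, and section 7.4.1 compares stroke severity and history between arms. Section 7.3 calls the study a pilot.

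Most of this stands as mitigation. It does not stop a physician who can see the arm from reading a vague exclusion differently on even days. The blinded interviewer protects measurement, not entry, and a baseline table can show an imbalance without correcting it. Section 3.1 also calls the study phase III.

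Four stronger readings are tempting, and the documents do not support them.

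- *Patients are screened differently by arm.* Section 3.1.1 describes one eligibility process for all. The nurse's even-day query reads mainly as a way to reach her patients within the 24 hours set in section 5.1; nothing says that it feeds enrolment.
- *Half the 15-point target could be an artefact.* Dropping 10% of even-day patients, all non-adherent, gives 0.65 / 0.90 = 72.2%, or +7.2 points. That requires removing 10/35 = 28.6% of all non-adherent patients on one day type. Adherence is first measured 7 days after discharge, so nobody can select on it directly.
- *Allocation is really 2:3.* This follows only if weekdays are numbered 1 to 5. Section 6.2 refers to the admission date and section 7.3 to 1:1, which point to the calendar date. The wording needs reconciling, no more.
- *Ignoring clustering by day invalidates the tests.* With about 2.45 patients per weekday (372/152) and an assumed within-day correlation of 0.01 to 0.05, the design effect is 1.02 to 1.12 and true alpha 5.3% to 6.4%.

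**Conclusion.** The concern holds. The claim of stratified random assignment is wrong as written: the rule is predictable, unconcealed and without strata, and the workload cap can override it. Selective enrolment is possible when eligibility is judged, and the plan has nothing that would prevent it and little that would detect it.

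The documents do not show that bias will occur. Its size is unknown and rests wholly on assumption. In the illustration, mild selection (a tenth of the low-adherence group) is negligible. Screening out half of that group on even days roughly doubles the false-positive rate, with a spurious difference under a quarter of the 15-point target (3.3/15 = 22%).

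**What to change.** **Preferred.** Use a computer-generated list held outside the admitting team. Time-stamp eligibility in REDCap, which the study already uses, before the arm is revealed. Keep one identical screening log for all admission days, with reasons for exclusion. State that patients who overflow the nurse's caseload cap are recorded and analysed in the arm to which they were first allocated.

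**If parity is kept.** Delete the stratified-random claim and call the study quasi-randomized. Reconcile the weekday wording in sections 3.1 and 3.1.3 with the admission date in section 6.2, including weekend admissions. Keep the same log, and report eligible and enrolled counts by day parity. Prespecify adjustment for baseline variables already collected, for example stroke severity and age. The overflow rule is needed here too. Adjustment helps only with measured differences.

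**Either way.** If allocation is by day, standard errors clustered on admission date can be a sensitivity analysis.

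**Cost.** A protocol amendment, a list and a log; no added visits and no change in the sample-size formula. One drawback is that a random list produces runs of intervention assignments, which may reach the cap more often than near-alternating dates. Analysing overflow as first allocated then dilutes the effect, as the power figures above show, so the overflow count should be monitored and reported.
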